3.2 Study Design

This is a single-center, randomized controlled, open-label, pilot study to determine the feasibility of performing a larger multicenter phase III trial to assess the effects of UFH in ACS. Adult patients with SCD (HbSS, SC, or Sβ⁰) aged 18 years or older admitted to UPMC (Presbyterian, Montefiore, Magee, Shadyside) hospitals with a diagnosis of ACS will be eligible for screening to participate in the trial. Subjects meeting inclusion and exclusion criteria and consenting to study will be randomized within 24 hours of diagnosis to one of two treatment arms, Arm A, anticoagulation and standard of care, or Arm B, no anticoagulation and standard of care. Weight-adjusted UFH will be given at doses of 80 units per kilogram followed by 18 units per kilogram per hour intravenously for 7 days, or until discharge, if discharge is shorter than 7 days. UFH will be monitored by standard protocol to maintain the anti-Xa UFH level in the therapeutic range per institutional guidelines.¹⁵ During the study period, if therapeutic anticoagulation is indicated for non-research purposes, it will be given at the discretion of the treating physician.

Standard of care, per the treating physician, will include the following:

- Intravenous fluids, preferably hypotonic saline, will be given to maintain adequate hydration. The specific rate, subsequent changes in rate, and duration will be per the treating physician's discretion.
- Antibiotics will be given to treat pathogens that are responsible for community acquired pneumonia, such as "atypicals" or, if necessary, to provide a broader spectrum of coverage against antimicrobial organisms as the treating physician sees fit.
- Supplemental oxygen will be provided to maintain the arterial oxygen saturation, as recorded by pulse oximetry, greater than or equal to 90%.
- Incentive spirometry will be provided with recommendations to take 10 breaths every 2 hours while awake.
- Pain management will consist of acetaminophen, nonsteroidal antiinflammatory drugs (NSAIDs), or opioids as needed to maintain adequate analgesia. Specifics regarding pain management will be individualized according to each patient's established plan of care as dictated by his or her outpatient hematologist.
- Red blood cell transfusions will be given routinely as standard clinical practice in acute chest syndrome with the goal of preventing progression to acute respiratory failure.

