Further data collected will include information regarding standard of care therapy (collected daily during duration of study), demographics (collected following study enrollment and screening), and medical information (collected following study enrollment and screening). Regarding standard of care therapy, data collected will consist of whether or not intravenous fluids were given; whether or not antibiotics were administered, number of antibiotics received, and class of antibiotics given (penicillin, cephalosporin, macrolide, fluoroquinolone, vancomycin, other); whether or not supplemental oxygen was received with documentation of need for noninvasive positive pressure ventilation or mechanical ventilation; whether or not pain medication was provided, including type of pain medication (opioid, NSAIDs, acetaminophen, other); number of red blood cell transfusions given; and whether or not exchange transfusion was necessary. Demographics include age, race, and sex. SCD related medical information includes number of previous episodes of ACS, current administration of outpatient hydroxyurea, and prior DVT or PE. General medical information includes history of myocardial infarction; chronic lung disease, defined as a documented baseline arterial oxygen saturation less than 90% and/or home supplemental oxygen requirement; previous stroke; and current or former smoker.

Prespecified feasibility criteria are as follows: the ability to enroll potential study participants, which includes the timely notification of hospitalized patients with ACS, the capacity to consent eligible individuals, and the ability to appropriately randomize screened patients within 24 hours of diagnosis, all of which should occur at a frequency greater than or equal to 80%; inclusion and exclusion criteria that does not exclude potential study participants at a frequency greater than or equal to 20%; the proper administration of the study drug at a frequency greater than or equal to 90%; and the ability to completely and accurately collect clinical data of interest at frequency greater than or equal to 90%. The final aim of our pilot study is to provide preliminary data, with respect to treatment effect and variance, for future sample size calculations given the lack of existing data to help guide this process.

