The primary clinical outcome is duration of hospitalization. Secondary clinical outcomes include the duration of hypoxemia, duration of fever, duration of leukocytosis, duration of moderate to severe pain, total dose of opioids, and the number of red blood cell transfusions administered. Additional clinical outcomes will include the rate of transfer to the ICU, requirement for mechanical ventilation, and development of MODS.

Duration of hospitalization will be defined as beginning with randomization and measured in hours. Conclusion of hospitalization will be defined as the time of order entry into the inpatient electronic medical record system stating the patient is appropriate for medical discharge, per the discretion of the treating physician. Duration of hypoxemia will be defined as beginning with randomization and measured in hours. Hypoxemia will be defined as arterial oxygen saturation less than 90% according to pulse oximetry and/or the continued need for supplemental oxygen. If the patient's baseline arterial oxygen saturation is less than 90%, hypoxemia will be defined as a decrease in arterial oxygen saturation below the patient's baseline. Similarly, if

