the patient has a baseline supplemental oxygen requirement, hypoxemia will be defined as an increase in supplemental oxygen requirement above the patient's baseline. If the patient does not meet criteria for hypoxemia following the initial 3 nursing vital signs assessments after randomization, hypoxemia will be considered absent and no further assessments will occur. Resolution of hypoxemia will be defined as failure to meet the criteria for hypoxemia on 3 consecutive nursing vital signs assessments. Duration of fever will be defined as beginning with randomization and measured in hours. Fever will be defined as a body temperature greater than or equal to 38.0 degrees Celsius measured by a thermometer orally. If the patient does not meet criteria for fever following the initial 3 nursing vital signs assessments after randomization, fever will be considered absent and no further assessments will occur. Resolution of fever will be defined as failure to meet the criteria for fever on 3 consecutive nursing vital signs assessments. Duration of leukocytosis will be defined as beginning with randomization and measured in hours. Leukocytosis will be defined as a white blood cell count greater than 10,000 per liter. If the patient does not meet criteria for leukocytosis following the initial 2 complete blood counts after randomization, leukocytosis will be considered absent and no further assessments will occur. Resolution of leukocytosis will be defined as failure to meet the criteria for leukocytosis on 2 consecutive complete blood counts. Duration of moderate to severe pain will be defined as beginning with randomization and measured in hours. If the patient does not report a score of 4 or greater on the VAS for pain following the initial 2 assessments after randomization, moderate to severe pain will be considered absent and no further assessments will occur. The end of the duration of moderate to severe pain will be defined as 2 consecutive scores of less than 4 on the VAS for pain. Total dose of opioids will be defined as beginning with randomization, ending with study completion, and measured in milligrams of oral morphine equivalents. Red blood cell transfusions will be given routinely as standard clinical practice in acute chest syndrome with the goal of preventing progression to acute respiratory failure. Number of red blood cells transfused will be defined as beginning with randomization, ending with study completion, and measured in units of packed red blood cells received. Red blood cell transfusions given for suspected or proven hemorrhage secondary to UFH will not be included in the outcome as defined above. Rate of transfer to the ICU, requirement for mechanical ventilation, and development of MODS will be defined as beginning with randomization, ending with study completion, and categorized as present or absent. Further, MODS will be defined as the acute development of 2 or more organs or organ systems unable to maintain homeostasis in a critically ill individual.

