
Potential adverse events include heparin-associated risks, such as allergic reaction, major bleeding, minor bleeding, thrombocytopenia, and heparin induced thrombocytopenia (HIT), or any other adverse reaction suspected secondary to drug administration. All subjects enrolled in the study and received any UFH will be included in the safety evaluation.

A member of the research staff will collect the study data. All data required by the study protocol will be documented in the inpatient electronic medical record system. De-identified subject information will be written on Case Report Forms (CRFs) and all data collected will be stored in locked files at the Hemophilia Center of Western Pennsylvania (HCWP). Additionally, data will be entered into research electronic capture (REDCap) and compared to ensure consistency. No personal identifiers will be associated with the data. The Institutional Review Board (IRB) may inspect records at any time.

A sample size of 20 subjects for the pilot study is based on clinical rather than statistical considerations and should provide a preliminary estimate of primary and secondary clinical outcomes and assess prespecified feasibility criteria as detailed above. Based on 75,000 to 100,000 African Americans with SCD in the United States who develop ACS at a frequency of 8.8 per 100 patient years, with 50% developing ACS at some point during his or her lifetime, and given the fact that approximately 30 patients are admitted annually at UPMC hospitals (Presbyterian, Montefiore, Magee, Shadyside) with ACS, we estimate that at least 80%, or 24 patients per year, will meet inclusion and exclusion criteria, and expect to enroll 10 patients, or slightly less than 50% per year, which should meet the n=20 subjects required for the pilot study.^{3,4} This is a pilot feasibility study, so comparisons will be descriptive, including frequencies and percentages for categorical variables and mean, median, range, and standard deviation for continuous variables.

Demographics and medical information will be summarized with descriptive statistics as well. Adverse events will be summarized by frequency, relatedness, and severity.

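### Total opioid dose is summarized without any record of usual opioid dose, so a chance imbalance between arms of 10 would go unseen and the SD may be larger than it need be

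*Combined protocol and SAP*

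**What the plan says.** Section 3.3 names six secondary clinical outcomes, ending with "duration of moderate to severe pain, total dose of opioids, and the number of red blood cell transfusions administered". It defines the opioid outcome as a cumulative amount: "Total dose of opioids will be defined as beginning with randomization, ending with study completion, and measured in milligrams of oral morphine equivalents". Conversion to morphine equivalents puts different opioids on one scale. It does not refer the total to what the patient usually takes.

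Section 3.2 does not standardize analgesia: "Specifics regarding pain management will be individualized according to each patient's established plan of care as dictated by his or her outpatient hematologist".

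The disease-specific baseline items are few: "SCD related medical information includes number of previous episodes of ACS, current administration of outpatient hydroxyurea, and prior DVT or PE". Footnote 3 of Table 1 repeats them with the general medical history. Neither list contains usual opioid dose. The daily standard-of-care data record only whether pain medication was given and of what type.

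Section 4.2 allocates 10 patients to each arm and names no stratification factor. Section 3.3 limits comparisons to descriptive statistics, with no covariate adjustment. The same section wants treatment effect and variance from the pilot for sizing a later trial.

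**The concern.** If in-hospital dosing follows a plan set before admission, part of the variation in total opioid dose reflects who the patient is and not how the episode went. Two things follow.

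First, a few patients with high usual doses can fall unevenly into arms of 10. The raw difference could then look like a heparin effect, or conceal one, and a reader of the pilot report would have no baseline row to show it.

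Second, the SD reported for this outcome contains between-patient variation that a baseline covariate might remove. Effect and variance are stated products of the pilot, so this bears on what is handed to phase III, even though no hypothesis is tested.

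**Working it through.** **Plan's own figures.** There is none for this outcome: no SD, effect size, alpha, power, or share of patients on long-term opioids. The total of 20 has no statistical derivation: "A sample size of 20 subjects for the pilot study is based on clinical rather than statistical considerations". Its recruitment arithmetic is consistent: 30 × 0.80 = 24 eligible per year, 10/24 = 41.7% enrolled, 20/10 = 2 years.

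**Inputs.** From the documents: 20 patients, 10 per arm (section 4.2), and a schedule of 7 study days (Table 1). Assumed: number of usual-opioid users K, usual daily dose, and correlation r between usual and in-study dose.

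**1. Chance imbalance in users.** The number of users in one arm is hypergeometric. P(arms differ by at least 2) = 1 - P(most even split).

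| K of 20 | Calculation | Probability |
|---|---|---|
| 3 | 1 - 2·10·45/1,140 | 21% |
| 5 | 1 - 2·120·45/15,504 | 30% |
| 7 | 1 - 2·210·120/77,520 | 35% |
| 9 | 1 - 2·252·210/167,960 | 37% |
| 4 | 1 - 45·45/4,845 | 58% |
| 6 | 1 - 120·120/38,760 | 63% |
| 8 | 1 - 210·210/125,970 | 65% |

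Odd and even counts must be read separately. With even K, a difference of at least 2 means anything but an exact split. With odd K, the smallest difference is 1 and the next is 3. A difference of 4 or more has probability 9%, 14% and 17% for K = 4, 6 and 8.

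Treating usual dose as continuous avoids this parity effect. The SE of a difference in arm means is √(1/10 + 1/10) = 0.447 SD, so P(difference above 0.5 SD) = 2 × (1 - Φ(0.5/0.447)) = 26%, if the means are roughly normal.

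**2. Size of the shift.** Shift in arm means = (difference in users/10) × usual daily dose × 7. For a difference of 2 users at an assumed 50, 100 or 200 mg per day, this is 70, 140 or 280 mg. These are the most that the usual dose itself can contribute at that dose and split. They assume that it continues unchanged in hospital and that every patient stays 7 days; earlier discharge reduces them. With no SD in the documents, they cannot be judged large or small against the outcome.

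**3. Variance under two ways of using the baseline.** Regression adjustment leaves 1 - r² of the raw variance. The simple difference from usual dose leaves 2(1 - r), if both doses have equal SDs.

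| r | 1 - r² | 2(1 - r) | Later trial per arm, adjusted |
|---|---|---|---|
| 0.3 | 0.91 | 1.40 | 58 |
| 0.5 | 0.75 | 1.00 | 48 |
| 0.7 | 0.51 | 0.60 | 33 |
| 0.8 | 0.36 | 0.40 | 23 |

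The last column illustrates a true difference of 0.5 raw SD, two-sided 5% and 80% power. Unadjusted, 2 × (1.960 + 0.842)²/0.5² = 62.8, or 63 per arm; the adjusted entries multiply 62.8 by 1 - r² and round up.

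**4. Cost of adjusting in the pilot.** Residual degrees of freedom fall from 18 to 17. Estimating the slope multiplies the variance of the difference by about 1 + 1/(20 - 4) = 1.06. At r = 0.3 the net ratio is 0.91 × 1.0625 = 0.97, almost no gain. At r = 0.5 it is 0.75 × 1.0625 = 0.80.

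**The case against.** The strongest case against is that this is one of six secondary outcomes in a descriptive feasibility pilot. Any unmeasured binary factor is subject to the same imbalance in arms of 10, no outcome in the plan is covariate-adjusted, and nothing says that phase III will be sized on opioid dose. All of that stands, and it limits the weight of the point. The plan does, however, ask for effect and variance from the pilot, and it ties analgesia to a patient-specific plan without recording what that plan implies.

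A reader might infer more than the documents support:

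- **That the arm comparison is biased.** It is not. Randomization makes the raw difference unbiased in expectation, and the issue is chance imbalance and precision.
- **That the raw SD is wrong for planning.** It is the right SD for a later trial that analyses the raw total. It is only inefficient if that trial would adjust for baseline.
- **That imbalance is more likely than not.** This holds for even user counts only; odd counts give 21-37%.
- **That each long-term user adds the home dose every study day.** Section 3.2 individualizes analgesia to an outpatient plan. It does not say that home dosing continues or that the plan reflects daily use.
- **That the information is lost for good.** Section 4.4 keeps a linkage key, so a later chart look-up may be possible. The plan as written does not call for one.
- **That the hypoxemia definition exposes an inconsistency.** For patients with low baseline saturation, "hypoxemia will be defined as a decrease in arterial oxygen saturation below the patient's baseline". That rule decides who counts as hypoxemic. It is not covariate adjustment and is a weak parallel.

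**Conclusion.** The point holds as a cheap improvement in precision and interpretability, not as an error that invalidates any result. That the total is unadjusted, that usual dose is in neither baseline list, and that analgesia is individualized are plain from the text. The size of the effect is not. The imbalance probabilities rest on assumed user counts, the milligram shifts on assumed doses and full 7-day stays, and the variance gain on an assumed correlation. The gain is worthwhile from about r = 0.5 upward and negligible at r = 0.3. No change to the sample size, the primary outcome or the feasibility criteria follows.

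**What to change.** Add one item to the baseline data in section 3.3 and to Table 1 with its footnote 3: usual daily opioid dose before admission, in oral morphine equivalents, taken from the chart or the outpatient plan of care. Summarize it by arm.

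Keep the raw total. Beside it, report the arm difference adjusted for usual dose by ANCOVA, with its residual SD. Prespecify a scale that admits zero doses, such as the square root, or the log after adding a fixed constant. State that the residual SD is for use only if phase III plans a baseline-adjusted opioid outcome on that scale.

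Do not use the simple excess over usual dose for planning: with equal SDs it reduces variance only when r exceeds 0.5.

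The cost is one chart-based field, one further summary line, and one degree of freedom in a sample of 20. The documented home dose may be inexact for some patients, which would weaken the correlation and the gain. The change concerns data collection and analysis only and leaves analgesic treatment as it is.

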3.3 Data Collection and Statistical Considerations

Data collection is summarized in Table 1. Body temperature and pulse oximetry will be checked by the inpatient nursing staff at least three times daily, beginning with randomization and ending with resolution of fever and hypoxemia, respectively, or study completion. Body temperature and pulse oximetry orders will be entered into the electronic medical record by a member of the research staff if not already ordered as part of standard of care. Documentation will be entered into the electronic medical record in the form of a research progress note informing the treating physician of vital signs ordered for research purposes to avoid duplication of tasks. The visual analog scale (VAS) for pain will be assessed once daily beginning with randomization and ending with resolution of moderate to severe pain or study completion. Laboratory evaluation will include a complete blood count (white blood cell count, hemoglobin and hematocrit, and platelet count). Complete blood count (white blood cell count) will be obtained daily beginning with randomization and ending with resolution of leukocytosis or study completion. Complete blood count (hemoglobin, hematocrit, and platelet count) will be obtained daily beginning with randomization and ending with study completion in subjects receiving UFH. Anti-Xa UFH level will be ordered according to the heparin infusion protocol as detailed earlier in subjects receiving UFH. Complete blood count will be entered into the electronic medical record by a member of the research staff if not already ordered as part of standard of care. Documentation will be entered into the electronic medical record in the form of a research progress note informing the treating physician of laboratory studies ordered for research purposes to avoid repeat blood draws. All blood samples will be collected by the inpatient phlebotomy team or nursing staff and sent to the inpatient laboratory for analysis.

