4.6 Adverse Event Reporting

All adverse events (AE) experienced by study subjects are to be recorded on the CRF, regardless of the severity of the event or its relationship to study treatment. The AE reporting procedures are based on the CTCAE system, volume 4.03, 2010. Subjects will report any symptoms to the investigator, research staff, inpatient nursing staff, or treating physician. [name] will determine if symptoms qualify as an AE or SAE with confirmation by [name]. AEs will be classified as mild (does not interfere with routine activities), moderate (interferes somewhat with routine activities), or severe (impossible to perform routine activities). The following algorithm will be used to assess the causality of all AEs:

- **Not related:** The event can readily be explained by factors not involving UFH, and a temporal relationship with UFH does not exist.
- **Possibly related:** A clinical event, including laboratory test abnormality, with a reasonable time sequence to administration of UFH but which could also be explained by concurrent disease or other drugs or chemicals. Information on drug withdrawal may be lacking or unclear.
- **Probably related:** The temporal relationship between the administration of UFH is compelling, and the event cannot be explained by the subject's medical condition or other therapies.
- **Related:** The event follows a reasonable temporal sequence from the administration of UFH, follows a known or suspected response pattern to UFH, is confirmed by improvement upon stopping UFH, and reappears upon repeated exposure to UFH.

The investigator will follow up all AEs, regardless of severity, until satisfactory resolution. All subjects experiencing AEs will be monitored until symptoms subside and any abnormal laboratory values have returned to baseline, or until there is a satisfactory explanation for the changes observed, or until death, in which case a full pathologist's report will be supplied, if possible. Withdrawal from the clinical study and therapeutic measures shall be at the discretion of the investigator. As required by the IRB, if there is a serious, unexpected or adverse event that is determined to be associated with UFH, it will be reported to the IRB within 24 hours. If the event is not serious, unexpected or related to UFH, it will be reported within 5 days. All events must be assessed to determine the following:

- If the event meets the criteria for an SAE.

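### Safety is evaluated in UFH recipients with no by-arm adverse-event table, so bleeding, hemoglobin falls, thrombocytopenia and other adverse events have no stated concurrent background rate

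*Combined protocol and SAP*

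**What the plan says.** **Population and summary (section 3.3).** After listing heparin-associated risks, the plan states "All subjects enrolled in the study and received any UFH will be included in the safety evaluation". Later in the section, after the general statement that comparisons are descriptive, it adds "Adverse events will be summarized by frequency, relatedness, and severity". Arm is not mentioned in either sentence.

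**Recording (section 4.6).** Collection is not limited by arm: "All adverse events (AE) experienced by study subjects are to be recorded on the CRF". The definition of an adverse event in the same section refers to a subject given a pharmaceutical product. It does not say how this applies to Arm B.

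**Causality (section 4.6).** Every category is framed against UFH. An event is *not related* when "The event can readily be explained by factors not involving UFH, and a temporal relationship with UFH does not exist". An event is *possibly related* when its timing relative to UFH is reasonable but "which could also be explained by concurrent disease or other drugs or chemicals".

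**Exposure (section 3.2).** UFH runs "intravenously for 7 days, or until discharge, if discharge is shorter than 7 days". In either arm, "if therapeutic anticoagulation is indicated for non-research purposes, it will be given at the discretion of the treating physician".

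**Blood counts (section 3.3).** Hemoglobin, hematocrit and platelets "will be obtained daily beginning with randomization and ending with study completion in subjects receiving UFH". The schedule that also covers Arm B is the daily white-cell count, which ends once leukocytosis resolves and can end after two counts if leukocytosis is absent.

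**Both-arm outcomes (section 3.3).** Units transfused, ICU transfer, mechanical ventilation and MODS are counted from randomization to study completion, with no restriction by arm.

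**The concern.** The trial randomizes a concurrent untreated arm, records its adverse events, and then states a safety evaluation that does not call on it. A reader of the final report would see how many UFH subjects bled, lost hemoglobin or became thrombocytopenic, but not how often the same happened in comparable ACS patients without UFH. The documents give no figure for that background.

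This matters most where an event could arise without UFH. Section 4.4 grades bleeding as major on, among other criteria, a hemoglobin fall of 2 g/dL or more or transfusion of at least 2 units. Section 3.2 makes red cell transfusion routine care in both arms. Under section 4.5, major bleeding associated with UFH prompts a DSMC judgment on whether to continue. The pilot is also meant to inform a phase III trial, whose planners will want to know whether an observed rate is an excess.

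**Working it through.** **1. What has a comparator and what does not.**

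| Event | Stated in both arms? | Where |
|---|---|---|
| Units transfused | Yes, excluding those given for suspected or proven UFH hemorrhage | 3.3, secondary outcome |
| ICU transfer, mechanical ventilation, MODS | Yes | 3.3, additional outcomes |
| Bleeding, hemoglobin fall, thrombocytopenia, other adverse events | Recorded for all subjects (4.6); no by-arm summary stated | 3.3 |

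For adverse events the gap is therefore in analysis, not in collection.

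**2. Can causality ratings stand in for a control?** *Not related* has two conditions: another explanation, and no temporal relationship with UFH. Because the infusion continues up to 7 days or discharge, an Arm A event during infusion that ACS explains can, read as written, fail the second condition and be rated *possibly related*. The same event in an Arm B subject never given UFH can only be *not related*. The rating depends on exposure and is made unblinded, so it does not estimate a background rate.

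**3. The protocol's own rate on 10 subjects.** Section 4.2 puts 10 subjects in each arm. Section 4.4 quotes 5 to 30% for non-immune thrombocytopenia on heparin.
- Expected events: 10 × 0.05 = 0.5 and 10 × 0.30 = 3.
- Chance of at least one, 1 − (1 − p)^10: 40.1% at 5% and 97.2% at 30%.
- Exact (Clopper-Pearson) 95% interval for 3/10: 6.7% to 65.2%.

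**4. What Arm B adds.** Take 3/10 on UFH against assumed Arm B counts, with Newcombe 95% intervals built from Wilson limits (l, u) for each arm: lower = d − √[(p1 − l1)² + (u2 − p2)²]; upper = d + √[(u1 − p1)² + (p2 − l2)²]. For 3/10 v 0/10 the Wilson limits are (0.108, 0.603) and (0, 0.278). The lower limit is 0.30 − √(0.192² + 0.278²) = −0.04 and the upper is 0.30 + 0.303 = 0.60.

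| Arm B (assumed) | Difference, points | 95% interval |
|---|---|---|
| 0/10 | +30 | −4 to +60 |
| 1/10 | +20 | −16 to +51 |
| 2/10 | +10 | −26 to +44 |
| 3/10 | 0 | −36 to +36 |

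The same UFH count can mean a large apparent excess or none.

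**5. Limits of that gain.** Zero events in 10 has an upper 95% limit of 1 − 0.025^(1/10) = 30.8%. Fisher's two-sided test with 10 per arm gives p = 0.087 for 4 v 0 and p = 0.033 for 5 v 0. Power at 30% v 0% is therefore P(X ≥ 5 | n = 10, p = 0.30) = 15%.

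**6. Events from background alone (assumed rates).** Suppose a fraction b of ACS patients without UFH has a hemoglobin fall of 2 g/dL or more, or receives 2 or more units. The chance that at least one of 10 UFH subjects does so with no UFH effect is 1 − (1 − b)^10: 65.1%, 89.3%, 97.2% and 99.9% for b = 10, 20, 30 and 50%. Section 4.4 applies these criteria to grade bleeding, so these are chances of meeting the numerical criterion, not of being called a major bleed.

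**7. Unequal counting.** Required hemoglobin and platelet counts run to study completion only on UFH. In Arm B, required counts can end as early as the second day if leukocytosis is absent. This reads the leukocytosis threshold as per microliter; taken literally as printed, per liter, counts would continue in both arms. A by-arm laboratory table must therefore show how often each arm was counted.

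**The case against.** The safety sentence says UFH recipients are included; it does not say only they are. It may be meant to keep partly treated subjects in. The adverse-event summary comes in a later paragraph, after the statement that comparisons are descriptive, and Table 1 lists adverse events on Days 1 to 7 without an arm. In a two-arm trial a by-arm table is a natural expectation, and the DSMC reviews events with all other available data. That reading is possible. It does not displace the one population the plan states, and no sentence brings Arm B adverse events into the evaluation. Table 1 does not settle it either, since it lists anti-Xa levels without an arm although section 3.3 limits those to UFH subjects.

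Other parts of the opposing case stand and limit the point:
- A reader might infer that Arm B events go uncollected, or that nothing on UFH has a comparator. Section 4.6 and the four both-arm outcomes contradict this.
- A reader might infer a several-fold artefactual excess on UFH from unequal counting. On a 7-day stay with uniform onset and no standard-care counts, the ratio would be 7/2 = 3.5 only if all Arm B counts stopped on Day 2, and 1.0 if none stopped early. The documents do not give the share stopping early, and section 3.3 anticipates counts ordered as standard care. No fold figure is supported.
- A reader might infer that relatedness must always favor attribution to UFH. That depends on reading temporal relationship as mere overlap with the infusion.
- Arm B hemoglobin and platelet values are not clearly required on the CRF. Section 3.3 labels the shared count as the white-cell count, and the standard-care data list has no laboratory values.
- Safety comparison is not a stated aim, and 20 subjects was not chosen statistically.

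**Conclusion.** The point holds as a gap in the stated analysis. As written, the safety evaluation rests on UFH recipients and names no by-arm adverse-event summary. Bleeding, hemoglobin falls, thrombocytopenia and other adverse events on UFH then have no stated concurrent background rate, and UFH-only, open-label causality ratings cannot replace one. The change should be made, but the benefit is interpretive: with 10 per arm, 0/10 is compatible with a rate up to 31% and power for 30% v 0% is 15%, so no safety conclusion would follow from a test. The conclusion rests on taking the safety sentence as defining the population. If a by-arm table was always intended, the remedy is the same sentence of clarification. The Arm B counts in the difference table and the background rates in step 6 are assumptions.

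**What to change.** In section 3.3:
- Define the safety set as all randomized subjects.
- Tabulate adverse events by frequency and severity, descriptively, by arm as treated, with separate lines for bleeding, hemoglobin fall and thrombocytopenia.
- Show relatedness for UFH-exposed subjects only.
- Flag any Arm B subject given non-research anticoagulation, and state where that subject is counted.
- For laboratory-detected events, report the number of counts per subject by arm and compare over days counted in both arms.

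In section 4.6, state that the adverse-event definition applies to Arm B.

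The clinical adverse-event tables use events that section 4.6 already requires to be recorded. The laboratory comparison may need Arm B hemoglobin and platelet values extracted from counts already drawn. No additional blood draws or study procedures are needed. The cost is small tabulation and extraction work.
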